- RSV viral load AUC from immediately prior to first dose of study drug (baseline) until Day 10 and until Day 14.
- RSV viral load AUC in subjects assigned to a longer dosing duration, if dosing duration is increased by the IDMC, from baseline until 1 day (+2 days) after the last dose of study drug.
- Sequence changes (postbaseline) in the RSV polymerase L-gene and other regions (if warranted) of the RSV genome compared with baseline sequences.
- Acceptability and palatability of the lumicitabine formulation as assessed by the parent(s)/caregiver(s) eCOA.

Exploratory Endpoints

The exploratory endpoints of this study are:

- The duration and severity of signs and symptoms of RSV infection as assessed by the PRESORS questionnaire completed by the parent(s)/caregiver(s) in the eCOA device.
- Number of hours the subject's parent(s)/caregiver(s) missed from usual activities.
- Medical resource utilization.
- RSV infectious viral load as measured using a quantitative viral culture (plaque assay).
- RSV viral load as measured by qRT-PCR of mid-turbinate nasal swabs and endotracheal samples in intubated subjects.

Refer to Section 9, Study Evaluations, for evaluations related to endpoints.

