2.5. Study Day and Relative Day

Study Day 1 refers to the date of first study medication intake (reference day). All efficacy and safety assessments at all visits will be assigned a day relative to this date.

The relative day for a visit is defined as:

$$reldy = visit\ day - reference\ day + 1$$

for visits on or after the reference day, and

$reldy = \text{visit day} - \text{reference day}$

for visits before the reference day, where the reference day is the start of study medication.

There is no 'Day 0'.

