5.2. Primary Efficacy Endpoint(s)

5.2.1. Definition

RSV RNA will be measured in mid-turbinate nasal swab specimens using an RSV-A/B qRT-PCR developed by DDL Diagnostic Laboratory.

The primary endpoint is RSV RNA \log_{10} viral load (measured by qRT-PCR in the mid-turbinate nasal swab specimens) area under the concentration-time curve (AUC) from immediately prior to first dose of study drug (baseline) until Day 7.

The primary estimates of the $AUC_{1-7 \text{ Days}}$ will be derived from a mixed model (see section 5.2.3 for the detailed specification). No imputations of missing data from nasal swabs post-baseline will be done in this model, as this mixed model would allow to make inferences under the missing at random assumption.

Note that for the primary endpoint the following rules apply:

- Only values as provided by the central lab will be used.
- Baseline is defined as the last measurement before first intake. In case a result is available that is no later than 1 hour after treatment initiation this may be used but only if no pre-treatment observation is available.
- For all post-baseline analysis visits the RSV RNA log₁₀ viral load result of the swab that was performed at that day will be used.
- In case multiple nasal swabs were taken on a single day the maximum on the log scale will be used as the value for that subject.

As a sensitivity analysis, descriptive statistics will be provided for the viral load AUC between 0h and 144h (AUC_{0-144h}); calculated by the trapezoidal summation rule, based on date time of sampling, including the timepoints with (imputed) values available:

$$AUC_{0-144h} = \frac{1}{2} \sum_{i=1}^n (y_i + y_{i-1}) \times (t_i - t_{i-1})$$

where $i=1,2,3,\dots,n$ are the time points when post baseline samples are collected, y_i is the log 10 viral load at the time and t_i is the time in hours post baseline. y_0 is the (imputed) log 10 viral load at baseline, t_0 is time 0 and t_n is time 144h.

The following additional rules, on top of the rules of the primary analysis, will be applied to deal with missing values before calculating the Viral load AUC_{0-144h}:

- The value at time point 0h, if not exactly at 0h, will be calculated based on intrapolation between the last observed pre-dose value and the first observed post-dose value.
- The value at 144h, if not exactly at 144h, will be calculated based on intrapolation between the last observed value before 144h and the first observed value after 144h.

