5.2.3. Analysis Methods

Mean \log_{10} viral load values over time will be analyzed using a restricted maximum likelihood based repeated measures approach. Analyses will include the fixed, categorical effects of treatment, stratification factors, analysis visit, and treatment-by-analysis visit interaction, as well as the continuous, fixed covariates of baseline \log_{10} viral load and baseline \log_{10} viral load by-analysis visit interaction. An unstructured covariance structure will be selected. In case this model will not converge, the following list of covariance structures will be applied and a selection will be based on the Akaike Information Criterion for those that do converge:

- Unstructured [UN]
- Ante-dependence [ANTE(1)]
- Heterogenous Toeplitz [TOEPH]
- Heterogeneous CS [CSH]
- Heterogeneous AR(1) [ARH(1)]
- Toeplitz [TOEP]

The Kenward-Roger approximation will be used to estimate denominator degrees of freedom. The testing of the dose-response relation is based on the expectation that higher dose regimens will be at least as efficacious as lower dose regimens with respect to efficacy on the viral load over time. Therefore, two contrasts on the dose regimens have been selected that are consistent with this expectation:

- a contrast with no difference between the 2 active regimens tested against placebo and
- a contrast with a positive linear dose-response relationship with respect to active regimens.

A multiple comparison approach will be taken testing the 2 contrasts combined versus placebo, adjusted for multiplicity.

The SAS mock code used to test the primary hypotheses will be as follows:

```
proc mixed data=viral_load;
  where avisitn in (2,3,4,5,6,7)
  class avisitn trt usubjid stratum;
  model logtiter = trt|avisitn stratum base|avisitn /ddfm=kr s;
  repeated avisitn/subject=usubjid type=un;
  lsestimate trt*avisitn
  "Plateau" -4 2 2 -4 2 2 -4 2 2 -4 2 2 -4 2 2 -2 1 1,
  "Linear" -4 0 4 -4 0 4 -4 0 4 -4 0 4 -4 0 4 -2 0 2
  /divisor=4 adjust=simulate seed=3369 alpha= $\alpha$ * lower cl;
run;
```

The variable *trt* denotes the *placebo*, *low dose regimen*, and *high dose regimen* treatment groups, the *avisitn* variable denotes the swabbing visits at Days 2 through 7, and the *base* variable is the baseline \log_{10} viral load measured at Day 1.

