5.3.1.1. RSV RNA \log_{10} viral load (qRT-PCR)

Table 1: Calculations and Conversion Formulae

Measurement	Formula
\log_{10} viral load actual values	\log_{10} of the actual values as measured with qRT PCR
\log_{10} viral load	Change = \log_{10} viral load actual value – \log_{10} baseline value

change from baseline	
Peak viral load	Highest value of \log_{10} viral load at or after the baseline measurement. The first record in time with this highest value is selected. This can be the baseline record or an unscheduled record.
Rate of decline of viral load over the first 24 hours	Calculated as a log decline/24 hours defined as: (24-hour log viral load after first dose of study drug – log viral load at baseline) / (date/time of 24-hour viral load sample – date/time of baseline viral load) Note, the 24-hour viral load may not have been measured at exactly 24 hours following first dose, but the actual date/time associated with the 24-hour viral load will be used in computing the viral load slope. In case the 24 hour measurement is not available the slope will be calculated using the Day 3 assessment (48 hours), using the same definition. If there is no measurement in that time frame, the slope will not be calculated.
RSV viral load AUC_{0-240h} RSV viral load AUC_{0-336h} [trapezoidal method]	Idem as RSV viral load AUC_{0-144h} from 0 hours until 144 hours using the trapezoid method (sensitivity analysis), but from 0 hours until 240 hours and 336 hours respectively.
RSV viral load AUC_{0-xxh} [trapezoidal method]	Idem as RSV viral load AUC_{0-144h} using the trapezoid method, but from 0 hours until xx hours, where xx will be calculated as 24 times the number of days with treatment + 1 day.
Time to peak viral load (hours) [Time-to event]	The time from initiation of study treatment until the first time point with the peak viral load (= event). Subjects for which the peak was reached at the baseline measurement will have time 0. Subjects for whom the peak is reached at the last observed time point will be censored at that time point. Subjects for which this last assessment is the baseline assessment will be censored at time 0. (Date and time of event or censoring - date and time of first dose of study drug)/3600, rounded to one decimal.

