5.3.2.1. RSV RNA \log_{10} viral load qRT-PCR

Log₁₀ Viral Load

Descriptive statistics and mean (SE) graphs will be shown of the \log_{10} viral load actual values and changes from baseline. For exploratory purpose the \log_{10} viral load actual values and changes from baseline will also be shown by sampling method (measured in the mid-turbinate nasal swabs and endotracheal samples from intubated subjects).

Differences on RSV RNA \log_{10} viral load by qRT PCR between treatment groups and by analysis visit will be determined by using appropriate contrasts in the mixed model in which the primary endpoint is modelled. Nominal 95% confidence intervals will be used.

Peak viral load; Rate of decline

The Rate of decline of viral load over the first 24 hours will be analyzed using descriptive statistics including the geometric mean and the coefficient of variation (CV).

The log peak viral load and rate of decline of RSV RNA viral load will be compared for active groups versus placebo groups using a general linear model with treatment and strata included as fixed effects.

Residuals of the final model will be plotted in a normal probability plot.

In case the model does not fit the log peak value data well, the log transformation (ie. the log of log peak viral load) will be considered as dependent variable. The data from the model will be reported as (adjusted) differences in least squares (LS) means (in the case of untransformed data) or (adjusted) geometric mean ratios (in case of log-transformed data) of active dose groups versus placebo, including 95% confidence intervals using appropriate contrasts.

RSV viral load AUC's.

The same model used for the primary analysis will be used to test for a dose response relationship on the viral load AUC until Day 10, until Day 14 and until 1 day after last dose for subjects with treatment extension (if applicable) (respectively $AUC_{1-10Days}$, $AUC_{1-14Days}$ and $AUC_{1-xxDays}$). No corrections for multiplicity will be made, thus the significance level of alpha (α^*) will be kept at 0.05. The differences in these AUCs for active versus placebo will be derived using appropriate contrasts deriving least square mean differences, including the 95% 2 sided confidence intervals.

The sensitivity analysis will be similar as for the primary endpoint, using the calculated viral load AUCs per subject based on the trapezoidal method (AUC_{0-240h} , AUC_{0-336h} and AUC_{0-xxh}) as indicated in section 5.3.1.1.

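### The per-subject AUCs that check the Day 10 and Day 14 viral load endpoints run to 240 h and 336 h, which are nominal Day 11 and Day 15 on the SAP's own day scale

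*SAP*

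**What the plan says.** The protocol (2.1.2, secondary endpoints) lists "RSV viral load AUC from immediately prior to first dose of study drug (baseline) until Day 10 and until Day 14". SAP 5.3.2.1 applies the primary model to the AUC "until Day 10, until Day 14 and until 1 day after last dose for subjects with treatment extension" and labels the first two AUC(1-10Days) and AUC(1-14Days). The same section names trapezoidal AUCs per subject, AUC(0-240h) and AUC(0-336h), as the sensitivity analysis. Table 1 in SAP 5.3.1.1 defines these like the 0-144 h AUC, "but from 0 hours until 240 hours and 336 hours respectively".

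The time scale is set elsewhere in the SAP. Section 2.5 says "Study Day 1 refers to the date of first study medication intake (reference day"), and adds that there is no Day 0. Section 5.2.1 defines the primary endpoint "from immediately prior to first dose of study drug (baseline) until Day 7" and pairs it with the trapezoidal version: "As a sensitivity analysis, descriptive statistics will be provided for the viral load AUC between 0h and 144h". Table 1 itself, on the rate of decline, says that when the 24-hour sample is missing "the slope will be calculated using the Day 3 assessment (48 hours").

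**The concern.** The hour limits for Day 10 and Day 14 look like 24 x 10 and 24 x 14, whereas the limit for Day 7 is 24 x 6. The two rules cannot both hold on one day scale. The end hour is also a real integration limit: under SAP 5.2.1 the value there is interpolated between the swabs on either side, or the last value is carried forward if no later swab exists.

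A sensitivity analysis should change the method and keep the quantity. With an extra day in the trapezoidal AUC, part of any disagreement with the model AUC would come from the window and not from the handling of missing data or sampling times.

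**Working it through.** **Rule.** With first dose on Day 1 and no Day 0 (SAP 2.5), nominal hours = 24 x (Day - 1).

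**Reproducing the SAP's own figures.**
- Day 3: 24 x 2 = 48 h, as in SAP 5.3.1.1.
- Day 7: 24 x 6 = 144 h, as in SAP 5.2.1.
- Model contrast (SAP 5.2.3): after the leading minus sign, the plateau coefficients read "4 2 2 -4 2 2 -4 2 2 -4 2 2 -4 2 2 -2 1 1", with divisor 4. Day weights are therefore 1 for each of Days 2 to 6 and 0.5 for Day 7. A trapezoid also gives 0.5 to baseline, which is a model covariate and cancels from treatment differences. The total is 0.5 + 5 + 0.5 = 6 days = 144 h.

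**Same rule for the secondary endpoints.**
- Day 10: 24 x 9 = 216 h. Trapezoid weights over swab Days 1-7 and 10 are 0.5, 1, 1, 1, 1, 1, 2, 1.5, which sum to 9 days = 216 h.
- Day 14: 24 x 13 = 312 h. Adding the Day 14 swab gives 0.5, 1, 1, 1, 1, 1, 2, 3.5, 2, which sum to 13 days = 312 h.

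The SAP prints coefficients only for Days 2-7. The model spans for Days 10 and 14 are inferred from the labels and from extending those weights.

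**Stated limits.**
- 240/24 + 1 = Day 11. Excess (240 - 216)/216 = 11.1%.
- 336/24 + 1 = Day 15. Excess (336 - 312)/312 = 7.7%.

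**End values for a subject with swabs on schedule.**
- At 240 h, weight on the Day 14 swab: (240 - 216)/(312 - 216) = 24/96 = 25%.
- At 336 h, with Day 28 at 24 x 27 = 648 h, weight on the Day 28 swab: (336 - 312)/(648 - 312) = 24/336 = 1/14, about 7%. If there is no later swab, the Day 14 value is carried forward.

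**Absolute AUC.** The documents give no decline curve. Assume log10 viral load falls linearly from v0 at rate r per day to a floor of 0. The AUC to T days is then v0 x T - r x T²/2 until T = v0/r, and constant at v0²/(2r) afterwards. In log10 x days:

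| v0 | r | to 216 h | to 240 h | excess | to 312 h | to 336 h | excess |
|---|---|---|---|---|---|---|---|
| 6 | 0.3 | 41.85 | 45.00 | 7.5% | 52.65 | 54.60 | 3.7% |
| 6 | 0.5 | 33.75 | 35.00 | 3.7% | 36.00 | 36.00 | 0% |
| 7 | 0.3 | 50.85 | 55.00 | 8.2% | 65.65 | 68.60 | 4.5% |
| 7 | 0.5 | 42.75 | 45.00 | 5.3% | 48.75 | 49.00 | 0.5% |

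**Treatment difference.** The extra day adds about 1 day x (active minus placebo mean log10 viral load) at Day 10-11 or Day 14-15. This is zero if the arms have converged. The documents give no figure for that difference.

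**The case against.** The strongest defence is that until Day 10 means ten elapsed days, or the end of calendar Day 10. Relative day is counted by date, so a Day 10 swab can fall anywhere from 192 h to 240 h after first dose. But either reading would make Day 7 168 h and Day 3 72 h, and the SAP uses 144 h and 48 h. Late visits do not explain the extra day either: the Day 7 analysis window also runs two days late, to Day 9, and its limit is still 144 h.

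Some of the other side stands. The trapezoid uses actual sampling times, while the model uses analysis visits with wide windows (Day 10 to 12 for Day 10, Day 12 to 20 for Day 14). The two would not cover identical time even at 216 h and 312 h. The SAP also states no intent, so keeping 240 h and 336 h with an open statement that they mean nominal Day 11 and Day 15 would remove the contradiction, though not the mismatch with the endpoint.

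Two stronger readings are tempting. A reader might infer that the Day 14 AUC depends materially on the Day 28 sample. For an on-schedule subject, the Day 28 value has 1/14 weight in one end point of one 24 h trapezoid: 12 h x 1/14 = 0.86 h out of 336 h, or 0.26% of the total weight. The Day 14 visit may also be up to two days late, and a swab on Day 15 or 16 falls at about or after 336 h, so Day 28 then adds little or nothing. A reader might also infer that treatment effects are inflated by the percentages in the table. Those describe absolute AUC within one arm, whereas the supportive analysis estimates differences versus placebo (SAP 5.2.3, carried over by 5.3.2.1).

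**Conclusion.** The inconsistency is real and no text in either document explains it. The AUCs labelled 0-240 h and 0-336 h run one nominal day past the endpoints they support. Hour equivalents are nominal, assuming swabs at about the same time each day, as the SAP's own 48 h and 144 h do.

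The consequence is limited. Absolute AUCs are overstated by 3.7-8.2% (Day 10) and 0-4.5% (Day 14) under the assumed curves. The effect on differences versus placebo is probably small, because all arms gain the same day. Only sensitivity analyses of secondary endpoints without multiplicity correction are touched. Nothing supports extending the point to the primary endpoint, the primary test or AUC(0-144h), all of which are on the correct scale. This is a minor consistency correction.

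**What to change.** In SAP 5.3.1.1 (Table 1) and 5.3.2.1, replace AUC(0-240h) with AUC(0-216h) and AUC(0-336h) with AUC(0-312h), on the same rule as AUC(0-144h), before unblinding. The cost is two constants and their labels in the SAP and the program. No new data are needed, and the protocol wording can stay.

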- d. The results of clinical/safety evaluations that are performed as part of routine clinical care while hospitalized will be collected in the eCRF for viral, safety, and/or clinical evaluation.
- e. Procedures performed as part of standard of care within approximately 72 hours prior to screening completion (ie, randomization) may be used in determining study eligibility.
- f. One LD followed by 9 MDs twice daily. MDs may be extended to up to 19 doses over 10 days if recommended by the IDMC.
- g. Study drug LD should be given as soon as possible but no later than 4 hours after randomization. Subjects will be dosed with a single LD followed by 9 MDs twice daily (minimum 8 hours and maximum 16 hours apart with no more than 2 doses per calendar day) from Day 1 to Day 5/6 (depending on the timing of the LD). Lumicitabine may be given without regard to food. The date and time of dose administration, the date and time of food intake (limited to the food ingested within 30 minutes before or after study drug administration), and the type of food will be recorded in the eCRF.
- h. An electronic device will be provided to the parent(s)/caregiver(s) at screening and the investigator/study-site personnel will provide sufficient information to enable the parent(s)/caregiver(s) to complete the parent(s)/caregiver(s) eCOA. Parent(s)/caregiver(s) will complete the eCOA screening and twice daily for the entire duration of hospitalization, at approximately the same time each day. On the day of discharge, parent(s)/caregiver(s) will complete the eCOA before the subject leaves the hospital.
- i. The assessment on Day 1 must be recorded predose, before the LD. If the screening assessment was performed less than 8 hours prior to the LD, the predose assessment does not need to be performed.
- j. The first postdose assessment must be performed between 6 and 12 hours after the LD (on Day 1 or Day 2, depending on the time of LD).
- k. Clinical evaluation includes, but is not limited to, RSV disease symptoms, vital signs, oxygen requirement (type and duration), level of hospital care, duration of hospitalization, respiratory rate, body temperature, and SpO₂.

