performed on the contralateral nostril. Nasal swabs and endotracheal samples should be frozen as soon as possible after being collected. The actual times of sample collection and sample freezing must be recorded in the eCRF. Should the study drug duration be increased to up to 10 days (following review of the data by the IDMC), samples will be taken every day up to and including 1 day (+2 days) following the last dose of study drug. Quantitative culture of RSV using plaque assay may be performed centrally at timepoints selected by the virologist.

- t. Mid-turbinate nasal swabs and/or endotracheal sample must be taken as close as possible to and before the LD on Day 1.
- u. Only 1 blood sample will be collected if the biochemistry and hematology analyses are performed on the same day.
- v. A urinalysis can be performed during the screening period or on Day 1 prior to the LD dose. A sample will also be collected on the last day of dosing, within 3 hours of the last dose.
- w. At randomization, each subject will be randomly assigned to 1 of 2 PK sampling schemes, Group X or Y, with 3 PK timepoints per group: 2 samples will be taken on Days 1 to 2 and 1 random PK sample will be taken on Day 7. The actual dates and times of sample collection must be recorded in the eCRF. The IDMC may recommend that only 2 PK samples be used under the conditions of footnote w.
- x. The IDMC may recommend that only 2 PK samples (post Dose 1 and Day 7) be collected after at least 9 subjects have completed treatment with the 60 mg/kg LD/40 mg/kg MD lumicitabine regimen if the Option A design is chosen or after at least 9 subjects in each cohort have completed treatment with the highest active lumicitabine regimen available in their respective cohort if the Option B design is chosen. The post Dose 2 sample will not be collected in this scenario.

TIME AND EVENTS SCHEDULE: AFTER HOSPITAL DISCHARGE

Phase Day	Treatment Phase 3 to 6 ^b	Follow-up Phase ^a						
		7 ^c (+2 days)	8 to 9	10 (+2 days)	11 to 13	14 (+2 days)	15 to 27	28 (±2 days) EoS
Study Procedure								
Screening/Administrative								
Body weight		X		X		X		X
Body length and head circumference								X
Study Drug Administration ^d								
Dispense/administer study drug ^e and study medication log	X							
Clinical Efficacy Evaluations								
Parent(s)/caregiver(s) eCOA ^f	bid	bid	bid	bid	bid	bid	X	X
Clinical evaluation and clinician eCOA ^g		X		X		X		X
Oxygen saturation (SpO ₂)		X		X		X		X

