10	10	Day 10	[10,12*]
14	14	Day 14	[12*,20]
$+\infty$	28	Day 28	[21, $+\infty$ [

¹ Records before the datetime of first intake only.

² As calculated according to the baseline definition.

³ Includes only the post-dose records.

* Depending on the VISIT label, the measurement of subjects returning on Day 12 should be assigned to Day 10 or Day 14. In case the VISIT label equals Day 12 the measurement will be allocated to Day 10.

For the analyses of measurements scheduled once daily the following rules will be applied in order to have only one evaluation per subject per analysis visit:

1. If two assessments fall within the same interval, the measurement closest to the target day will be used.
2. If the assessments are equidistant, the last measurement within the interval will be used.
3. If there are two measurements on the same date and time, then the measurement with the highest sequence number will be used.

An exception will be made:

1. In case multiple nasal swabs were taken on a single day, the maximum viral load on the log scale will be used as the analysis value for that subject on that day.

For the analysis of measurements scheduled more than once daily (vital signs: twice daily and SpO₂: every 4 hours / every 8 hours), the assessments will be allocated to analysis time points as described in the table below based on the actual time of the measurement. In case there is more than one assessment per analysis time point window, the mean of these assessments will be calculated in order to have only one evaluation per analysis timepoint.

Analysis time point (numeric version)	Analysis time point	Time Interval (hour:min)
Vital sign assessments *		
1	Morning]02:00, 14:00]
2	Evening]14:00, 02:00]
SpO ₂ **		
0	Morning]0:00, 08:00]
8	Midday]08:00, 16:00]
16	Evening]16:00, 0:00]

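### If the IDMC extends dosing, the extended-dosing viral load AUC cannot be analysed as written: the main model lacks the visits it needs, and the sensitivity window has no settled end

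*SAP*

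**What the plan says.** Protocol 2.1.2 lists as a secondary endpoint the "RSV viral load AUC in subjects assigned to a longer dosing duration, if dosing duration is increased by the IDMC", running "from baseline until 1 day (+2 days) after the last dose of study drug". The Time and Events Schedule for hospitalised subjects sets the maximum extension (footnote f): "MDs may be extended to up to 19 doses over 10 days if recommended by the IDMC". Under extension (footnote s, and Protocol 9.1.3), "samples will be taken every day up to and including 1 day (+2 days) following the last dose of study drug".

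The SAP analyses this endpoint in two ways.

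- **Main analysis.** SAP 5.3.2.1 applies the primary mixed model to the AUC "until 1 day after last dose for subjects with treatment extension", labelled AUC(1-xxDays). That model works by analysis visit. SAP 2.1 allocates every parameter to analysis visits: one window for each of Days 2 to 6, then Day 7 (Days 7 to 9), Day 10 (Days 10 to 12) and Day 14. Day 12 records go to Day 10 or Day 14 according to their visit label. For once-daily measurements one record is kept per window: "If two assessments fall within the same interval, the measurement closest to the target day will be used".
- **Sensitivity analysis.** SAP 5.3.2.1 continues: "The sensitivity analysis will be similar as for the primary endpoint, using the calculated viral load AUCs per subject based on the trapezoidal method". For the extended case this is AUC(0-xxh). SAP Table 1 (5.3.1.1) ends its window at xx hours, "where xx will be calculated as 24 times the number of days with treatment + 1 day".

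**The concern.** Protocol 11.10 lets the IDMC and Sponsor Committee extend dosing without a protocol amendment, so the SAP has to work on the day that happens.

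In the main analysis, the extra daily swabs asked of infants under extension would largely not reach the endpoint they serve, and the model would have no estimate at the day where that endpoint ends.

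In the sensitivity analysis, the AUC is a total over time, not an average. If its window follows each child's own treated days, a child who stops early accumulates less AUC simply because less time is counted. Lower AUC reads as better antiviral effect, so the artefact would favour whichever arm had more early stopping.

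**Working it through.** **1. The SAP's own figure.** The Table 1 rule is xx = 24 × days + 24. For the standard 5 days, 24 × 5 + 24 = 144 h, which is the window in SAP 5.2.1. For 10 days, 24 × 10 + 24 = 264 h. Under the day numbering in SAP 2.5, 144 h after the first dose falls on Day 7 (144/24 + 1) and 264 h on Day 12 (264/24 + 1).

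**2. End day of the model-based AUC.** Ten days is 1 loading and 19 maintenance doses, at most 2 per calendar day. With two doses on Day 1, the 20th falls on Day 10 and the endpoint ends on Day 11. With one dose on Day 1, the 20th falls on Day 11 and the endpoint ends on Day 12.

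**3. Swabs that reach the model.** Daily swabs on Days 2 to 11 make 10.

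| Analysis visit | Swab days in window | Kept | Dropped |
|---|---|---|---|
| Days 2 to 6 | one each | 2, 3, 4, 5, 6 | none |
| Day 7 | 7, 8, 9 | 7 | 8, 9 |
| Day 10 | 10, 11 | 10 | 11 |

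Seven are kept and 3 dropped. A Day 12 swab goes to the Day 10 window, where the Day 10 swab is nearer the target, or to Day 14, by its label. The exception for several swabs on one day does not help, because these fall on different days. The visits go from Day 10 to Day 14, so neither Day 11 nor Day 12 has a model term. Stopping the contrast at Day 10 would reproduce AUC(1-10Days), which is listed separately.

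**4. Window length if xx follows actual days.** 3 treated days: 24 × 3 + 24 = 96 h. 5 days: 144 h. 7 days: 192 h. 10 days: 264 h.

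**5. Effect on one child's total AUC.** The documents give no rate of viral decline, so the curves below are assumptions. The same curve is integrated to the shorter window and to 264 h. For a linear fall from 6 to 3 log10 over 264 h, A(T) = 6T − 3T²/(2 × 264). Then A(264) = 1,188 and A(144) = 746.2, and the shortfall is 1 − 746.2/1,188 = 37.2%.

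| Assumed curve | Stop after 3 days | After 5 days | After 7 days |
|---|---|---|---|
| Flat | 63.6% | 45.5% | 27.3% |
| 6 to 3 log10 over 264 h | 55.9% | 37.2% | 20.7% |
| 6 to 0 log10 over 264 h | 40.5% | 20.7% | 7.4% |
| 6 to 0 log10 by 168 h | 18.4% | 2.0% | 0.0% |

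**6. From one child to an arm.** With equal curves, the shift in an arm's mean, as a share of a completer's AUC, is about the between-arm difference in the proportion stopping times the shortfall. For an illustrative 10-percentage-point difference, all stopping after 3 days, it is 0.10 × 63.6% = 6.4% (flat) down to 0.10 × 18.4% = 1.8%. After 5 days it is 4.5% down to 0.2%. With equal stopping rates and times it is about zero.

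**The case against.** The best defence is that xx is a placeholder for the duration the IDMC chooses. The protocol defines the population by assignment to longer dosing. Extension is up to 10 days, so a number could not be written in advance. AUC(1-xxDays) uses the same symbol in a mixed model whose contrast needs common visits and cannot vary by child. The 144 h window applies to every child whatever doses were taken. This stands as a plausible reading, but it is not the only one. The protocol ends the endpoint relative to the last dose, SAP 4.3 writes planned where planned is meant, and SAP 4.4 defines treatment duration from actual first and last intake. The wording is ambiguous.

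It is also fair that AUC to Day 10 and Day 14 already provide fixed windows over much of this period. They do not supply the endpoint that the protocol defines.

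A reader might infer four stronger points, which the documents do not support:

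- That early stopping is scored as efficacy in the trial's main results. The artefact can arise only in a sensitivity analysis, and only on the actual-days reading.
- That the trapezoidal AUC also loses swabs. SAP 5.2.1 builds it from sampling dates and times. Its remark that its missing-value rules come on top of the primary rules leaves slight doubt, but the plain reading is that no swab is lost.
- That an evening loading dose lengthens the window by 24 h. This assumes calendar days are counted. A standard course may run to Day 5 or Day 6, and the SAP still uses 144 h for all.
- That the shortfalls in the working can be set against the assumed 20% to 30% drug effect. That effect (SAP 1.4) is a group mean for the 7-day AUC on the high dose, whereas the shortfalls belong to single children.

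**Conclusion.** Both gaps are real and conditional on extension. The visit-window gap follows directly from the text: 3 of 10 daily swabs on Days 2 to 11 do not enter the main analysis, and its end day has no visit. It needs no assumption beyond a 10-day extension with swabs taken as scheduled.

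The window-end gap is an ambiguity with a possible bias. If xx means actual days, the total AUC of an early stopper is lower by 0% to 64% over the curves and stopping times shown. The size rests on assumed viral decline, and any bias between arms rests on unequal stopping.

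Importance is limited. The endpoint is secondary, has no multiplicity control and exists only if the IDMC extends dosing. The primary AUC(1-7 Days) is unaffected. It is worth settling because the repair is cheap and extension needs no protocol amendment.

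**What to change.** 1. **SAP 2.1 and 5.3.2.1.** When extension is in force, add separate viral load analysis visits for Days 8, 9, 11 and 12, with the Day 12 visit taking precedence over the Day 10/Day 14 label rule. Write out the AUC(1-xxDays) contrast weights to one common end day for the assigned duration. For 10 days, Day 12 would match 264 h. Children whose last dose is on Day 10 may have no Day 12 swab and would then enter under the model's missing-at-random assumption.
2. **SAP Table 1.** Define xx as 24 × assigned days + 24 h, for every child in every arm, whatever doses were taken. This gives 264 h for 10 days, is consistent with 144 h for 5 days, and still works if the IDMC chooses a shorter extension.

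The cost is SAP wording and programming for the extension case, with no new samples. The downside is that, after early discontinuation, follow-up visits come 2, 5 and 9 days after the last dose (Protocol 9.1.4). For a child whose last dose is on Day 3 these fall on Days 5, 8 and 12, each with up to 2 days' allowance. The later part of the window for such children would therefore rest on sparser swabs and interpolation.
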